**1. ABSTRACT**

**Background:**

[figure not shown]
Cholestasis is a condition characterized by impairment of bile flow and/or formation. The condition can occur from either extrahepatic obstruction or intrahepatic hepatocyte bile secretory defects.

Cholestatic liver diseases are a well-recognized cause of dyslipidemia, and are closely associated with abnormal cholesterol and phospholipid metabolism. Cholesterol conversion to bile acids may be impaired, and apo-lipoprotein B binding to cholesterol may be impaired, resulting in the formation of lipoprotein X which contains apolipoprotein C. The end result of dyslipidemia in cholestatic patients is hypercholesterolemia and an increased membrane cholesterol to phospholipid ratio.

Elevated red cell membrane cholesterol to phospholipid ratios result in decreased osmotic fragility and decreased deformability of the red blood cell (RBC). When red cell membranes are compromised, and especially when membrane peroxidation is increased (due to exposure to an excessive oxidant load or due to reduction in antioxidants such as vitamin E), spur cells will form (1,2).

We hypothesize that even in the absence of spur cell formation, subclinical changes in osmotic fragility will appear and these can be measured by ektacytometry.

Ektacytometry is a tool to measure the deformability and osmotic fragility of red blood cells subjected to shear stress while exposed to an osmotic gradient (Figure 1). Ektacytometry can be used as a diagnostic tool to determine the presence of abnormalities in cell membrane structure. It does this by analyzing the RBC rheological behavior in a variety of physiologic and non-physiologic conditions.

**Figure 1. Normal RBC ektacytometry.** The curve provides the following characteristics: **Elongation Index (Elmax):** Elmax corresponds to the maximum deformability of the erythrocyte. Its value depends mostly on the cytoskeleton mechanics. **Omin:** Omin corresponds to the value of the hypotonic osmolality where 50% of the cells hemolyze in an osmotic fragility assay and provides information on the initial surface to volume ratio of the cell sample. A shift to the right reflects a decrease in the surface area/volume ratio. **Ohyp:** The declining portion of the curve is represented by the Ohyp value. This is the osmolality value where the cell's maximum diameter is half of Elmax and correlates with the initial intracellular viscosity of the cell sample. A shift to the left reflects increased intracellular viscosity of the erythrocyte caused by increased intracellular concentration of hemoglobin and/or a dehydration state.

### Objective:

We propose to perform ektacytometry on 20 pediatric patients over age one with cholestatic liver diseases and a direct bilirubin level of greater than 2 gm/dl. The most common diagnoses will be extrahepatic biliary atresia, progressive familial intrahepatic cholestasis, Alagille syndrome, autoimmune hepatitis, primary sclerosing cholangitis, and parenteral nutrition-associated cholestasis. We will correlate the osmotic fragility and deformability with their direct bilirubin levels, their serum cholesterol levels, their serum bile acid levels, and their vitamin E levels.

### Design/Methods:

This pilot study will be a single center, prospective cross-sectional investigation of red blood cell ektacytometry in pediatric patients with extrahepatic cholestasis who are followed at Cincinnati Children's Hospital Medical Center. We will include all subjects with cholestasis regardless of the etiology in order to maximize the number of subjects. While the population will be heterogeneous, we will stratify patients according to diagnosis, recognizing that only a few patients may fall into each diagnostic category. Ektacytometry will be the method utilized to measure osmotic fragility and deformability of the RBC membrane. The ektacytometry of red cells from cholestatic patients will be compared to that of red cells obtained from contemporaneous age-matched controls recruited among patients without liver disease or red cell membrane defects undergoing blood sampling for evaluation of other entities including but not confined to functional abdominal pain.

## 2. PURPOSE OF STUDY

### Primary Aim:

The primary aim is to determine if ektacytometry of red blood cells is abnormal in a population of pediatric patients over age one with cholestasis.

### **Secondary Aims:**

The secondary aim is to ascertain the extent at which abnormalities in bilirubin levels, bile acid levels, vitamin E levels or cholesterol levels in cholestatic patients are related to changes in red blood cell ektacytometry in this patient population.

### **3. BACKGROUND**

Cholestatic liver disease is an umbrella term for reduced bile flow from either extrahepatic obstruction of bile ducts or faulty hepatocyte bile secretion. Cholestasis is a well-recognized cause of dyslipidemia, and are closely associated with abnormal cholesterol and phospholipid metabolism (3). Cholesterol conversion to bile acids may be impaired, and apo-lipoprotein B binding to cholesterol may be impaired, resulting in the formation of lipoprotein X which contains apo-lipoprotein C (3). The end result of dyslipidemia in cholestatic patients is hypercholesterolemia and an increased membrane cholesterol to phospholipid ratio (3).

The lack of bile entering the digestive tract can lead to increased serum cholesterol, and abnormally high red cell membrane cholesterol: phospholipid ratios, resulting in altered red cell membrane structural integrity (4,5). To test for this phenomenon in patients with extrahepatic biliary atresia, 20 pediatric patients will be tested using ektacytometry to test the deformability and osmotic fragility of red blood cells.

Ektacytometry is a diagnostic tool used to measure the deformability of red blood cells on an osmotic gradient (6). More specifically it measures deformability due to shear stress, while the RBC are suspended in an osmotic medium (6,7). It can differentiate among several blood maladies such as hereditary spherocytosis, hereditary elliptocytosis, Southeast Asian ovalocytosis, and pyropoikilocytosis that are otherwise difficult to diagnose (8). It does this by analyzing their rheological behavior under constant shear stress in vitro and using photometric analysis of deformability. This is then quantified and provides a specific ektacytometry curve (Figure 1).

The ektacytometry curve will have several unique features depending on the red blood cell being analyzed. The Omin portion of the curve represents the value of the osmolality in which 50 percent of the red blood cells lyse. The Elmax is the value of the elongation index that reaches its maximum near physiologic osmolality (300 mOsm/Kg). And lastly the Ohyp, which represents the declining portion of the curve and correlates to the initial intracellular viscosity of the cell sample.

To date, ektacytometry has not been employed systematically to characterize potential red cell abnormalities in cholestatic patients. In our analysis the ektacytometry profiles of cholestatic patients will be compared to those of historical non-cholestatic age-matched controls. The degree of fragility will be correlated with serum direct bilirubin levels, serum cholesterol levels, and vitamin E levels.

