### **4. STUDY DESIGN**

This pilot study will be a single center, prospective cross-sectional investigation into the ektacytometry of red blood cells taken from 20 cholestatic pediatric patients followed at Cincinnati Children's Hospital. They are seen regularly for continued follow up in the hepatology clinic. Parents of all of these patients will be asked to participate in this investigation. We will also contemporaneously analyze ektacytometry of 20 age-matched controls recruited from the general GI clinics with neither cholestatic liver disease nor known red cell membrane defects.

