### **Controls**

Parental refusal  
Age <1 year old.  
Known congenital red cell membrane defect  
Cholestatic liver disease

The study Principal Investigator (PI), PI designate, or research coordinator (research team) will have the responsibility for case finding and subject recruitment. Potential study participants will be identified by the PI and a further member of the research team will enroll the participants.

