## **8. STUDY PROCEDURES**

All patients are routinely seen in outpatient clinic by one of the hepatologists from Cincinnati Children's Hospital Medical Center. Control patients will be gastroenterology patients seen by one of the general gastroenterologists in the general gastroenterology clinics. The research team will approach the family in clinic or in the hospital and after informed consent will obtain a 500-1500 mcl aliquot left-over from blood that has been drawn into a lavender top (EDTA) tube for measurement of a complete blood count. or a yellow top tube for measurement of serum chemistries. To avoid research-only blood draws, blood will only be obtained if the patient is undergoing clinical laboratory testing. The team's PI, [name], and coinvestigators, [name] and [name], will have access to the individual results of the assay.

All blood samples will be de-identified with the assigned research number.

In addition to providing a blood sample, we will record in a secure database the patient's demographics such as current age at time of blood draw, race and ethnicity, birth history, past medical and surgical history as well as contemporaneous direct bilirubin levels, hemoglobin levels, hematocrit levels, and red cell morphologic changes noted in the hemogram. Cholesterol levels, bile acid levels, and vitamin E levels which were obtained as close as possible to the ektacytometry analysis will also be recorded. Only the investigators at Cincinnati Children's will have access to this database.

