### **Laboratory Methods:**

Within 24 hours of blood sampling, we will conduct our ektacytometric analysis. Samples will be drawn into EDTA tubes. In the clinical hematology lab, hemoglobin, hematocrit, red cell indices, and RBC number will be measured by standard methods. A blood smear will be stained with a Giemsa stain and reviewed by clinical cytologists. Ektacytometry will be performed in the CCHMC Erythrocyte Diagnostic Lab per clinical testing SOP. Specifically, a 300 microliter sample will be injected into the Osmoscan LoRRca MaxSis (Mechatronics Instruments BV, Zwaag, The Netherlands) ektacytometer. Patients' RBCs deformation will be monitored while exposed to a constant shear stress of 30 Pa and an increasing osmotic gradient in

order to generate the ektacytometry curves. A positive result is seen as a divergence of the Omin, Elmax, and Ohyp of the sample compared to a concurrently-run normal control and the normal control range for the assay. Deformability will also be tested under an increasing shear stress for further investigation of the RBC cytoskeleton mechanics. The Erythrocyte Diagnostic Lab will then discard the remaining sample once a result is obtained.

Bilirubin levels, bile acid levels, lipid profiles, and vitamin E levels will be measured by standard laboratory methods employed by the CCHMC clinical laboratory. Bile acids will be measured by radioimmunoassay.

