### **10. FACILITIES AND PERFORMANCE SITES**

The research study, all patient recruiting and blood draws will be performed in either the inpatient hepatology unit, the hepatology clinic, the general GI unit, or one of the general GI clinics at CCHMC. Ektacytometry will be performed in the CCHMC Erythrocyte Diagnostic Laboratory and analyzed by [name]. Bile acids will be analyzed within [name] laboratory.

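### Does the word *historical* in the Background leave the control group for the patient-control comparison undefined?

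*Protocol*

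**What the plan says.** Three places in the Protocol describe when the comparison group is obtained.

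- Section 3 (Background), last paragraph: "In our analysis the ektacytometry profiles of cholestatic patients will be compared to those of historical non-cholestatic age-matched controls".
- Section 1 (Abstract), Design/Methods: patients' red cells will be "compared to that of red cells obtained from contemporaneous age-matched controls recruited among patients without liver disease or red cell membrane defects".
- Section 4 (Study Design): "We will also contemporaneously analyze ektacytometry of 20 age-matched controls recruited from the general GI clinics".

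Other sections describe the controls without using either time label. Section 6 gives them their own inclusion and exclusion lists, and the exclusions include "Parental refusal". Section 8 takes control patients from the general gastroenterology clinics and adds: "The research team will approach the family in clinic or in the hospital and after informed consent will obtain a 500-1500 mcl aliquot". Section 9 (Sample size) plans 20 cholestatic patients and 20 controls. Section 9 (Statistical analysis) compares Omin and Elmax means between patients and controls by Student's t test and does not say again which controls are meant.

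**The concern.** A control group is either taken from past data or enrolled and assayed alongside the patients. The Protocol says one thing in Section 3 and the other in the abstract and Section 4. The Section 3 sentence cannot be dismissed as a remark on the literature: it is in the future tense, it concerns this study's own analysis, and the sentence after it sets out planned correlations that Section 9 repeats.

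The choice would matter if it were really open. With historical controls, any change over time in the assay, in sample handling or in the patients seen at the centre would be mixed with the effect of cholestasis. Enrolled controls assayed over the same period largely remove that problem. The t test paragraph names no control type, so it does not settle the question by itself. Someone who read only Section 3 would describe the study as historically controlled.

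**Working it through.** No arithmetic applies. The Protocol gives no effect size, standard deviation or power, and Section 9 says that a power analysis cannot be done. The size of any bias from historical controls cannot be derived from the document either. The check is a comparison of every place that describes the controls.

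| Place in the Protocol | What it says about controls | Historical or enrolled? |
|---|---|---|
| Abstract, Design/Methods | Contemporaneous, recruited, having blood taken for other reasons | Enrolled |
| Section 3, last paragraph | "will be compared to those of historical non-cholestatic age-matched controls" | Historical |
| Section 4 | 20, recruited from general GI clinics, assayed contemporaneously | Enrolled |
| Section 6, control criteria | Own eligibility lists; refusal by a parent excludes | Enrolled |
| Section 8 | Patients of the general gastroenterology clinics; consent, then left-over blood | Enrolled |
| Section 9, Sample size | 20 controls planned beside 20 patients | Fits enrolled |
| Section 9, Laboratory Methods | A concurrently run normal control and the assay's normal range | Laboratory reference, a separate use |
| Section 9, Statistical analysis | Patients against controls, type not given | Neutral |

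**Count.** The word *historical* occurs once in the Protocol, in Section 3. *Contemporaneous* or *contemporaneously* is applied to the controls twice, in the abstract and in Section 4. Its use in Section 8 concerns laboratory values and is not counted.

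**Could both statements be true?** They could if a second, historical group were planned as well. Such a group would need a source, a number and a place in the analysis, and the Protocol gives none of these. The nearest candidate is the laboratory reference in Section 9, where a sample is judged positive when "compared to a concurrently-run normal control and the normal control range for the assay". That rule classifies a single sample. It is not described as an age-matched group and is not an arm of the t test.

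**What would an analyst do?** The only control data that the Protocol causes to exist are those of the 20 children enrolled under Sections 4, 6 and 8. The t test therefore runs on 20 + 20 = 40 children under either wording of Section 3.

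**Evidence given little weight.** Section 10 states that "all patient recruiting and blood draws will be performed in either the inpatient hepatology unit, the hepatology clinic, the general GI unit" or the general GI clinics. It never mentions controls, and a cholestatic patient could also be in a general GI unit, so it does not discriminate. Refusal by a parent is also an exclusion for the disease cohort. It helps only because it stands in the control list as well, where it would have no purpose for a historical series.

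**The case for a change.** The strongest case for a change is that the sentence is wrong as written. It is current text, it states the study's own plan, and the statistical paragraph does not override it. Stating the comparator is the protocol's job and is not normally left to an analysis plan. Correcting it would take a few words.

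Most of this stands. The contradiction is real, and it is not a product of text extraction, redaction or an amendment log. What does not stand is that it leaves anything undecided. Section 4 follows directly after the sentence and gives the source, number and timing of the controls. The link to the primary aim is also an inference, although a reasonable one: Section 2 asks whether ektacytometry is abnormal and names no comparator, and the Section 3 sentence does not mention the primary aim.

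One reservation runs the other way. The Protocol does not say how the assay's normal range was built. A loose reading, in which Section 3 meant that range or an additional comparison with it, is unlikely but cannot be excluded. Even on that reading, the enrolled controls and the t test stay as they are.

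**Conclusion.** The inconsistency exists but calls for no change to the plan. It is one word in the Background, and it is outweighed by the abstract, the Study Design section, the control eligibility lists and the study procedures. Its effect on recruitment, on the 20 + 20 sample size, on the t test and on the conclusions is nil. Replacing the word would tidy the text without altering anything that is done or reported.

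This rests on two assumptions. The first is that the operative sections express the intended design. The second is that no historical control series outside the Protocol was meant to enter the analysis. The document supports the first throughout and contains nothing against the second. If such a series were meant to enter the analysis, the design and analysis sections would have to describe it, and the point would need to be reopened.

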### **4. STUDY DESIGN**

This pilot study will be a single center, prospective cross-sectional investigation into the ektacytometry of red blood cells taken from 20 cholestatic pediatric patients followed at Cincinnati Children's Hospital. They are seen regularly for continued follow up in the hepatology clinic. Parents of all of these patients will be asked to participate in this investigation. We will also contemporaneously analyze ektacytometry of 20 age-matched controls recruited from the general GI clinics with neither cholestatic liver disease nor known red cell membrane defects.

## 5. DURATION

The study is anticipated to take approximately 6-12 months to complete. This time table includes 3-6 months to recruit patients and perform the assays and another 3-6 months to analyze the data and complete a manuscript.

## 6. SELECTION & RECRUITMENT OF PARTICIPANTS

- Inclusion Criteria

### **Disease Cohort**

Age greater than one year old  
Direct bilirubin level of >2 mg/dl.  
No known congenital red cell membrane defect

### **Controls**

Age matched to disease cohort  
No evidence for cholestatic liver disease  
No known congenital red cell membrane defect

- Exclusion Criteria.

### **Disease Cohort**

Parental refusal  
Age <1 year old.  
Known congenital red cell membrane defect

### **Controls**

Parental refusal  
Age <1 year old.  
Known congenital red cell membrane defect  
Cholestatic liver disease

The study Principal Investigator (PI), PI designate, or research coordinator (research team) will have the responsibility for case finding and subject recruitment. Potential study participants will be identified by the PI and a further member of the research team will enroll the participants.

## 7. PROCESS OF OBTAINING CONSENT

The Research Team will discuss appropriateness for study inclusion with the clinical team, and contact the family, most likely during their hepatology outpatient clinic visit or an inpatient hospitalization. The study will enroll children, a vulnerable population, therefore patients and parents will be explicitly informed that choosing not to participate, will in no way affect the quality of the medical care that they will receive.

Details of the study will be reviewed with one or both parents prior to obtaining consent. All patients will be under the age of 18 years old and therefore only parental consent will be necessary along with the participant's assent if older than 11 years of age.

## **8. STUDY PROCEDURES**

All patients are routinely seen in outpatient clinic by one of the hepatologists from Cincinnati Children's Hospital Medical Center. Control patients will be gastroenterology patients seen by one of the general gastroenterologists in the general gastroenterology clinics. The research team will approach the family in clinic or in the hospital and after informed consent will obtain a 500-1500 mcl aliquot left-over from blood that has been drawn into a lavender top (EDTA) tube for measurement of a complete blood count. or a yellow top tube for measurement of serum chemistries. To avoid research-only blood draws, blood will only be obtained if the patient is undergoing clinical laboratory testing. The team's PI, [name], and coinvestigators, [name] and [name], will have access to the individual results of the assay.

All blood samples will be de-identified with the assigned research number.

In addition to providing a blood sample, we will record in a secure database the patient's demographics such as current age at time of blood draw, race and ethnicity, birth history, past medical and surgical history as well as contemporaneous direct bilirubin levels, hemoglobin levels, hematocrit levels, and red cell morphologic changes noted in the hemogram. Cholesterol levels, bile acid levels, and vitamin E levels which were obtained as close as possible to the ektacytometry analysis will also be recorded. Only the investigators at Cincinnati Children's will have access to this database.

### **Study Completion**

Once the blood sample has been obtained, no additional study procedures will be performed and the remaining blood will be properly disposed once the assay is complete.

## **9. DATA ANALYSIS/METHODS**

### **Sample size:**

The sample size of 20 cholestatic patients and 20 controls is estimated based on the number of patients followed at CCHMC. We estimate a 75 % participation rate for the study. Knowing that we have a small patient pool within each diagnostic category of cholestatic patients, we will stratify patients according to diagnosis, but suspect that we will have only 3-5 patients within each diagnostic grouping, so it may be difficult to draw conclusions regarding relative differences in osmotic fragility and deformability within the overall cholestatic population. Because this is a pilot study we do not know what the difference in Omin or deformability between patients and controls will be. Hence we cannot conduct power analysis. However, we can utilize our preliminary data to facilitate power analysis for future studies.

